### 10.2 Statistical Hypotheses

The Null Hypothesis: There are no differences between baseline and follow-up visit intraocular pressure values

Alternative Hypothesis: There are differences between baseline and follow-up visit intraocular pressure values

### 10.3 Analysis of Datasets

Data will be pooled from all study sites for data analysis, unless otherwise specified. Study dataset will be generated (keypunched) from original (white) case report forms (CRFs) that have been reviewed and collected from clinical sites. Dataset will contain rows of individual subject data; each row will be clearly labeled with the study subject assigned study number and initials. Each column of the dataset will contain a specific parameter for all study subjects.

### 10.4 Description of Statistical Methods

#### 10.4.1 General Approach

Descriptive statistics (i.e., mean, standard deviation, etc.) will be provided for all continuous variables and frequency distributions will be generated for all categorical variables collected in this study. Analyses of the intent-to-treat (ITT) data set, will include all data from all subjects with a recorded screening visit IOP OU. Per protocol (PP) analyses dataset, will exclude data from subjects or visits with significant protocol deviations (e.g., IOPs obtained before 8:00 AM and after 10:00 AM will be excluded).

#### 10.4.2 Analysis of Primary Study Variable

The primary study outcome variable will be the change in IOP at Visits 4, 5, 6 and 7 (Days 7, 28, 60 and 90 days post-insertion) compared with the Baseline IOP (Visit 2, Day 0), obtained between 8:00 and 10:00 AM. The unit of analysis will be the study eye at visit 2 with the highest post-washout IOP. Observed IOP and percent change from baseline in IOP will also be analyzed.

#### 10.4.3 Other Data Endpoints

The following will be evaluated:

- Mean and percent change in Baseline IOP (post-washout) compared with Screening IOP (pre-washout)
- Mean and percent of patients screened vs patients that qualified for the study washout phase
- Mean and percent of patient entered in the washout phase that qualified for the treatment phase
- Evaluate enrollment rate of patients in to the various phases of the study (avg. number of patients by day/week/month)
- Mean and percent of patients and eyes with IOPs > 34 mmHg post-washout
- Mean and percent of patients and eyes that extruded a plug during the study treatment phase
- Mean and percent of patients and eyes the investigator was unable to dilate to at least 1.0 mm
- Mean and percent of patients and eyes the investigator was unable to insert with a Travoprost Evolute®
- Listing of reasons why patient failed to qualify for various phases of the study

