### **Study Outcome Endpoint:**

Primary Endpoint: Change in IOP from the baseline visit to Days seven, 28, 60 and 90.

Other Collected Data: Changes in IOP and percent change between the screening and the baseline visits (after washout phase, prior to insertion of any Travoprost Evolute®), percent of screened patients that qualified for washout phase, percent of patients that entered the washout phase that qualified for the treatment phase, enrollment rates (rates in to each phase of the study), number and percent of study subjects whose IOPs were  $\geq 34$  mmHg at Visit 2, number and percent of eyes that extruded a study plug, number of eyes investigators were unable to dilate or insert a study plug, listing of reasons why patients failed to qualify.

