## 5 STUDY ENROLLMENT AND WITHDRAWAL

### 5.1 Study Population

Up to 30 qualified male or female subjects (~30 qualified eyes) who have given HIPAA and informed consent, have met all screening and washout criteria, will be enrolled into the treatment phase of the study and have a Travoprost Evolute inserted into the lower punctum of each eye. All study plugs will remain in the study subject's lower puncta for a period of 90 ± 7 days after insertion.

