##### 5.4.2.1 Reasons for Discontinuation

A study subject will be discontinued from the study: a) if the Investigator is unable to sufficiently dilate the punctum or insert a punctal plug in to the lower punctum of either eye, b) if a subject has extruded a plug and a new plug cannot be re-inserted, c) if during the course of the study a subject has extruded a plug from each eye, d) if a subject has extruded a plug more than once from the same eye e) in a subject where only one eye qualified at Visit 2, if the plug is extruded in the qualified eye, f) if a subject has used a prohibited concomitant ocular or systemic (OTC/prescription) medication/therapy, g) if a subject is non-compliant and has missed scheduled study visits, h) for personal reasons, i) has relocated out of the area or has a desire to withdraw from further participation in the study in the absence of a medical need as determined by the Investigator. Other reason – the study subject was discontinued for a reason other than those listed above, the Investigator must specify the reason.

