##### 6.1.8.2 Extrusion of a Travoprost Evolute

A study subject that has noticed a study plug has been extruded or lost during the treatment phase, the study subject should immediately contact the Investigator and/or his/her staff and return to the Investigator's office as soon as possible. If the study subject can find the extruded plug, they should return with the plug where the Investigator and/or his/her staff will collect and retain the plug for investigational supply accountability. If the return plug has torn or has separated, report this as a technical complaint ([Section 8.6](#)). If a study plug has been lost, the Investigator will retro-illuminate or palpate the canaliculi to confirm the plug has not migrated into the canal. Information regarding the loss of any plug must be recorded in the source documents, CRFs and Accountability Logs.

If a single plug has been extruded during the study, the Investigator will re-insert a new plug and instruct the study subject to return to the investigator office based on their originally study visit(s) scheduled. At any time during the study, a study subject experiences a second extrusions or an extrusion in the fellow eye, the study subject will return to the Investigator's office as soon as possible and will have the remaining plug removed. The study subject will be discontinued from the study and **WILL** be replaced.

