## 6.2 Study Plug Accountability Procedures

The Investigator is responsible for maintaining the study treatment (punctal plugs) accountability log, which will contain inventory records acknowledging the receipt and dispensing of all study plugs. The study center will keep a complete accounting of all used, unused, damaged, extruded and lost study plugs. All lost/extruded study plugs must be recorded into the accountability log and on the CRFs of the study subject who lost/extruded a study plug, noting the suspected date the study plug was lost/extruded.

All used and unused study plugs must be accounted for and kept in the designated secure area at the study center until the Sponsor provides instructions for the return of all study materials. Final accountability for investigational study plugs will be verified by the Sponsor and/or their representatives and considered complete when the study plugs are no longer actively used and all study plugs (used, unused, extruded, lost) have been accounted for and returned to the Sponsor.

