#### 10.4.5 Adherence and Retention Analyses

Not Applicable

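### Plug extrusion is to be reported as a bare percent of patients and eyes, with no stated denominator and no allowance for wear time, so it reads low against 90 days of wear

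*Combined protocol and SAP*

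**What the plan says.** Section 10.4.3 lists "Mean and percent of patients and eyes that extruded a plug during the study treatment phase" among the other data endpoints. The Synopsis has the shorter form "number and percent of eyes that extruded a study plug", and Section 4.2.2 has a similar line. None of these gives a denominator, a time origin, a censoring rule or an interval.

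Intended wear is "for a period of 90 ± 7 days after insertion" (Section 5.1). Several rules end it sooner:

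- Section 5.4.1: plugs are removed at the subject's last visit, whether or not that visit was scheduled.
- Section 6.1.8.2: after a second extrusion, or one in the fellow eye, the subject "will have the remaining plug removed", is discontinued and is replaced.
- Section 5.4.2.1: discontinuation follows repeat loss from one eye, loss from each eye and, where only one eye qualified, "if the plug is extruded in the qualified eye". Prohibited medication, missed visits and withdrawal also lead to discontinuation.
- Sections 7.10.1 and 5.4.3.1: rescue use terminates the subject. Plugs are removed, and the subject is counted as a completer and not replaced.

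The dates needed for a time-based analysis are collected. The accountability log and CRFs record each loss, "noting the suspected date the study plug was lost/extruded" (Section 6.2). Section 11.1 item g asks for insertion, removal, loss and re-insertion dates.

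**The concern.** A plug removed intact on Day 20 because the subject needed rescue adds nothing to the numerator. If all inserted eyes form the denominator, it counts the same as a plug that stayed in place to Day 90. The Introduction presents the product as delivering drug for up to 90 days, so a reader will probably take the reported percent as the chance of losing a plug over that period. Unequal wear time pulls the percent below that chance, and more so as early exits increase.

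The unstated denominator is a second problem. Subjects discontinued for extrusion are replaced, and nothing says that they stay in the calculation. Extrusion is listed both as a secondary variable (Section 4.2.2) and as a safety variable (Sections 4.2.3 and 10.4.4), so a figure that is ambiguous and leans low deserves correction.

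**Working it through.** **Inputs.** The protocol states no extrusion rate, exit rate or share of subjects with one qualifying eye, and Section 10.5 has no sample-size calculation. There is no figure of the plan's own to reproduce. Assumed here: true 90-day loss per eye p = 20% or 30%, other exits by Day 90 e = 0 or 20%, constant hazards, and independent eyes unless stated. From the protocol: both eyes are plugged, so 30 subjects give up to 60 eyes before replacements. A first loss is re-inserted unless it is in the sole qualified eye. The subject stops at the second loss, or at loss from the sole qualified eye.

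**Step 1, patient percent (closed form).** With time in units of 90 days, the hazard of a first loss in either eye is λ = −2 ln(1−p), and the exit hazard is μ = −ln(1−e). The true patient loss is 1−(1−p)². The crude percent is λ/(λ+μ) × [1−exp(−λ−μ)].

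- p = 20%, e = 20%: λ = 0.446, μ = 0.223. True 36.0%; crude 0.667 × (1 − 0.64 × 0.8) = 0.667 × 0.488 = 32.5%. Low by 3.5 points.
- p = 30%, e = 20%: λ = 0.713, μ = 0.223. True 51.0%; crude 0.762 × (1 − 0.49 × 0.8) = 0.762 × 0.608 = 46.3%. Low by 4.7 points.

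With e = 0 the crude and true values agree. Removing the remaining plug after an extrusion cannot change the patient percent, because that patient is already counted.

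**Step 2, eye percent from exits alone.** The same formula with λ = −ln(1−p) gives 0.5 × (1 − 0.8 × 0.8) = 18.0% for p = 20%, and 0.615 × (1 − 0.7 × 0.8) = 27.1% for p = 30%.

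**Step 3, eye percent with the extrusion rules added.** Removal of the remaining plug hides something only after repeat loss from one eye or loss from the sole qualified eye. When the second loss is in the fellow eye, both eyes are already counted. Simulation of the rules (200,000 subjects per scenario, all inserted eyes in the denominator) gives:

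| True eye loss | Other exits | Crude eye %: both eyes qualify / half of subjects with one / all with one | Patient %: true → crude |
|---|---|---|---|
| 20% | 0 | 19.8 / 19.4 / 18.9 | 36.0 → 36.0 |
| 20% | 20% | 17.9 / 17.5 / 17.1 | 36.0 → 32.5 |
| 30% | 0 | 29.4 / 28.5 / 27.6 | 51.0 → 51.0 |
| 30% | 20% | 26.7 / 25.8 / 24.8 | 51.0 → 46.3 |

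In the middle case with 20% exits, the eye shortfall is 20.0 − 17.5 = 2.5 points and 30.0 − 25.8 = 4.2 points. Kaplan-Meier by eye returns the true value to within about 0.1 point.

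**Step 4, sensitivity.**

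- Early-clustered loss (Weibull shape 0.5 and 0.3; true patient loss 51.0%, 20% exits): crude reads 48.1% and 49.1%, low by 2.9 and 1.9 points.
- Correlated eyes (gamma frailty, variance 1; true eye loss 30.1%, 20% exits, half of subjects with one qualifying eye): crude 24.8%, Kaplan-Meier by eye 28.6%. By patient, true 46.4%, crude 42.5%, Kaplan-Meier 46.4%.
- Denominator: if subjects discontinued for extrusion are dropped altogether, a true 20% per eye with no other exits reads 15.4% (both eyes qualify) down to 9.2% (one eye qualifies in every subject).

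**Step 5, precision.** Exact 95% intervals, ignoring pairing of eyes: 12/60 eyes gives 10.8 to 32.3%, and 11/30 patients gives 19.9 to 56.1%.

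**The case against.** The endpoint is the percent that extruded during the treatment phase, and no 90-day rate is defined. With all inserted subjects in the denominator, the crude percent is a valid cumulative incidence in which early exit competes with extrusion. This stands: the percent is low only against loss over full 90-day wear. That target is still the more useful one, because removal of the remaining plug is a rule of the trial and not behaviour of the device.

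The bias lies inside the sampling error of about 60 eyes in an uncontrolled pilot. This also stands and limits how much weight the point can carry. The bias nevertheless runs in one direction, and no interval is planned that would show the uncertainty.

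Other summaries will show some of the losses. Plug position is graded at every treatment visit, Section 10.4.1 calls for frequency distributions of all categorical variables, and every loss is logged. So it cannot be said that re-inserted plugs go unexamined. None of these summaries accounts for wear time, however, and a second loss from the same eye adds nothing to a percent of eyes.

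Two stronger readings are tempting. A reader might infer from the not-applicable entry under "10.4.5 Adherence and Retention Analyses" that analysis of plug retention was waived. Section 5.3 uses retention to mean keeping subjects in the study, which is the natural sense here too. A reader might also take plug retention to be the main feasibility result. The documents do not say so: the stated objectives are pressure lowering and safety, and extrusion is one of nine items in Section 10.4.3.

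**Conclusion.** The point holds as a cheap improvement, not as a flaw that threatens the study. The plan leaves the extrusion denominator open and ignores unequal wear time. Against 90 days of wear, early exit for other reasons lowers both percents. Removal of the remaining plug lowers only the eye percent, and only after repeat loss from one eye or loss from the sole qualified eye.

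At an assumed true loss of 20 to 30% per eye with 20% other exits, the shortfall is about 2.5 to 4 points for eyes (half of subjects with one qualifying eye) and 3.5 to 5 points for patients. The patient figure falls to 2 to 3 points at the upper end if losses come early. These sizes rest entirely on assumed rates. Leaving replaced subjects out of the denominator could matter more (a true 20% reading 15.4 to 9.2%), but the plan does not say that it will do so. A reader might infer that plug removal understates loss for patients as well as eyes; Step 1 shows that it cannot.

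**What to change.** In Section 10.4.3:

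1. Keep the crude counts, with the denominator stated as all inserted subjects and all inserted eyes, including subjects later discontinued and replaced.
2. Add Kaplan-Meier time from insertion to first extrusion, by patient (first extrusion in either eye) and by eye, censored at plug removal or exit. Give the Day 90 estimate with a 95% interval, clustered by subject for the by-eye curve (subject-level bootstrap or robust standard error).
3. Report extrusions per 100 plug-days over every plug inserted, including re-inserted plugs, which cannot reach 90 days on the original visit schedule.
4. Note two limits: the by-eye curve can stay slightly low if a subject's two eyes are correlated, and loss dates are suspected dates.

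Section 6.1.8.2 (re-insertion after any single extrusion) conflicts with Section 5.4.2.1 item e and note D of the Schedule of Assessments (discontinuation when the sole qualified eye loses its plug). These passages must be reconciled, because they determine which eyes are censored and when.

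The cost is a short text change and some programming on dates already recorded. No new data are needed. The reported Day 90 loss will probably be a few points higher than the crude percent.

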#### 10.4.4 Safety Analyses

All subjects that qualify for the washout phase of the study will be evaluated. Safety variables will include any clinically significant changes in IOP, BCDVA, slit-lamp findings, ocular tearing and comfort, blood pressure, heart rate, temperature, study plug inspections/extrusions, and incidence and severity of any reported AEs/SAEs and ADEs/SADEs.

#### 10.4.5 Adherence and Retention Analyses

Not Applicable

#### 10.4.6 Baseline Descriptive Statistics

Demographic and baseline characteristics will be summarized. Counts and percentages will be presented for categorical variables such as gender, age group (by decade), race and ethnicity. Mean, standard deviation, median, minimum and maximum will be presented for continuous variables such as age and non-dilated punctum size.

#### 10.4.7 Planned Interim Analyses

Data will be analyzed on an ongoing basis. The final analyses will be completed after the last study subject has completed his/her final visit and the study database has been closed.

#### 10.4.8 Tabulation of Individual Response Data

Not Applicable

#### 10.4.9 Exploratory Analyses

Not Applicable

## **10.5 Sample Size**

Since this is a pilot study, no formal sample size estimation will be performed.

## **10.6 Measures to Minimize Bias**

Not Applicable.

### **10.6.1 Enrollment**

Each investigational site will be assigned a site ID number (e.g., 100, 200 . . . 500). As a potential study subject qualifies to enter the study washout period, they will be sequentially assigned a study number that corresponds with the site ID number (e.g., 101, 102, . . . 110). If the potential subject does not qualify after the washout period, the subject ID number will be retired. Those subjects that do qualify will be identified throughout the treatment period of the study by his/her assigned subject ID number and initials.

### **10.6.2 Evaluation of the Success of Blinding/Masking Treatment**

Not Applicable

## **11 SOURCE DOCUMENTS AND ACCESS TO SOURCE DATA/DOCUMENTS**

### **11.1 Source Documentation**

The Investigator must maintain adequate and accurate source documents upon which CRFs for each study subject are based. They are to be separate and distinct from the CRFs, except for cases in which the Sponsor has predetermined that direct data entry into specified pages of the subject's CRF is appropriate. Study source documents should include detailed notes on:

- a. Study protocol number
- b. The oral and written communication with the study subject regarding the study treatment (including the risks and benefits of the study).
- c. The date that informed consent and HIPAA forms were signed must be recorded in the source documentation
- d. The study subject's medical history prior to participation in the study
- e. The study subject's basic identifying information, such as demographics, that links the subject's source documents with the CRFs
- f. Date of all study subject visits throughout the duration of the study
- g. Date the punctal plug was first inserted, removed and if applicable, dates of any plug that was extruded/loss and a new plug was re-inserted
- h. Intraocular Pressure values and slit-lamp findings at each visit

- i. The subject's exposure to any concomitant therapy (including start and stop dates, route of administration, and dosage) at each visit
- j. Blood pressure, temperature and heart rate values at each visit
- k. All reported AEs/ADEs and SAEs/SADEs
- l. All relevant observations and data on the condition of the subject throughout the study

## **11.2 Access and Retention of Study Records**

The study is subject to audits by the Sponsor/designee, third parties, or by regulatory authorities. If such an audit occurs, the Investigator must agree to allow access to all required study subject records. The Investigator will notify Sponsor promptly of any FDA audits that are scheduled, and must forward copies of any resultant Form 483 and/or audit reports to the Sponsor promptly.

All study records will be maintained by the Investigator at the site for a minimum of 2 years following the date a marketing application is approved for the drug for which the indication was being investigated. If no application is to be filed or the application is not approved for such indication, study records must be retained for at least 2 years after the investigation is discontinued and the FDA is notified.

## **11.3 Subject Confidentiality**

All records identifying the study subject by name will be kept confidential. The Investigator will ensure the study subject's anonymity is maintained throughout the course of the study. A study subject will be assigned a site/subject ID number to maintain study subject confidentiality. In particular, the Investigator will keep an enrollment log with confidential identifying information that corresponds to the subject numbers and initials of each study subject. A study subject name may possibly be disclosed to Mati Therapeutics Inc. or regulatory agencies during inspection of medical records related to the study, but reasonable precautions will be taken to maintain confidentiality of personal information to the extent permitted by applicable laws and regulations. If the results of the study are published, the study subject's identity will remain confidential.

## **11.4 Case Report Form Completion**

The Investigator is responsible for ensuring that data are properly recorded on each study subject's case report forms and related documents. An Investigator who has signed the protocol signature page should personally sign completed case report forms to ensure that the observations and findings are recorded on the case report forms correctly and completely. Following study examination, investigative sites should complete and remove the yellow NCR copy of the CRF from the study subjects' booklet leaving the white copy of the CRF intact inside the booklet. Yellow copies of completed CRFs will be mailed in on a weekly basis to the following:

D'Ellis Group, Inc.  
Attn: [name]

[name]  
[name]

The white copy of the CRF data will be reviewed against the subject's source data by the study monitor(s) to ensure completeness and accuracy. After monitoring has occurred at the clinical site(s) and the CRFs have been submitted, additional data clarifications and/or additions may be needed. Data clarifications and/or additions are to be documented and will be part of each subject's CRFs.

### **11.5 Investigator Study Summary**

A final Investigator's summary will be provided to Mati Therapeutics Inc. within approximately three months after the completion of the study. The Investigator summary should include:

- a. Investigator name and title
- b. Title of the protocol
- c. Date the clinical study began (1st enrolled study subject) and the date the last study subject exited the study
- d. Number of study subjects enrolled into the study, completed, discontinued, terminated, withdrew
- e. Brief discussion regarding any reported AEs/SAEs and ADEs/SADEs
- f. Brief discussion of clinical findings during the study.

